4.1. Introduction

Data processing, tabulation of descriptive statistics, calculation of inferential statistics, and graphical representations, except for PK parameter estimation, will be performed primarily using SAS (release 9.4 or higher). All PK parameter estimations will be performed using WinNonlin® version 6.4 or later. If the use of other software is warranted, the final statistical methodology report will detail what software was used for what purposes.

For purposes of this SAP, “treatment within cohort” is defined as enrolled subjects (“Overall”) for Cohort 1 and treatment group (“ARQ-151 0.5%,” “ARQ-151 0.15%,” and “Vehicle”) for Cohort 2. For background and efficacy summaries for Cohort 2, this will be the randomized (ie, planned) treatment group; for safety summaries, this will be the actual (ie, received) treatment group.

Where possible, data for both cohorts will be summarized in the same output.

Continuous (quantitative) variable summaries will include the number of subjects (n) with non-missing values, mean, standard deviation (SD), median, minimum, and maximum.

Categorical (qualitative) variable summaries will include the frequency and percentage of subjects who are in the particular category or each possible value. In general, the denominator for the percentage calculation will be based upon the total number of subjects in the study population for the treatment groups within cohort, unless otherwise specified.

The minimum and maximum will be reported with the same degree of precision (ie, the same number of decimal places) as the observed data. Measures of location (mean and median) will be reported to 1 degree of precision more than the observed data and measures of spread (SD) will be reported to 2 degrees of precision more than the observed data.

Percentages will be presented to 1 decimal place, unless otherwise specified.

Unless otherwise indicated, all statistical tests will be conducted at the 0.05 significance level using 2-tailed tests, and *p* values will be reported. Corresponding 95% confidence intervals (CIs) will be presented for statistical tests.

4.2. Interim Analysis and Data Monitoring

No interim analyses are planned.

5. Analysis Populations

The following analysis populations are planned for this study:

- **Safety Population:** The Safety Population includes all subjects who are enrolled and received at least 1 confirmed dose of study medication in each cohort. This population will be defined separately for each cohort. Analyses using the Safety Population for either cohort will be based on treatment received.
- **Modified Intent-To-Treat (mITT) Population:** The mITT Population includes all subjects who are in the Safety Population for Cohort 2 with at least 1 post-baseline efficacy evaluation. Analyses using the mITT Population will be based on randomized treatment.
- **PK Population:** The PK Population includes all subjects, who consented to PK draws, receiving the active drug with sufficient plasma concentrations of roflumilast to define a profile, as determined by the pharmacokineticist. This population will be defined separately for each cohort. Analyses using the PK Population will be presented in a separate PK report, provided by the pharmacokineticist.
- **Per Protocol (PP) Population:** The PP Population includes all subjects who are in the Safety Population for Cohort 2, were at least on average 80% compliant with study medication, and showed no other serious deviations from the study protocol. Analyses using the PP Population will be based on randomized treatment.

6. General Issues for Statistical Analysis

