Study Procedure	Screen	Baseline	Week 1	Week 2	Week 3	Week 4	Week 4	Week 5
Weeks	-6	0	1	2	3	4		
Vehicle Application in Clinic (subject training) ^f			X ^f		X ^f			
Drug/Vehicle Application in Clinic ^g		X ^g		X ^g		X ^g		
ARQ-151 cream/Vehicle application at home		X	X	X ^h	X	X ^h		
Dispense study medication		X	X	X	X			
Weigh study medication		X	X	X	X	X		
Dispense/Review Diary		X	X	X	X	X	X ⁱ	
Adverse events assessments		X	X	X	X	X		
Concomitant medications	X	X	X	X	X	X		
Optional Skin biopsy ^j						X		
Telephone follow up ^j								X

^a Limited physical examination: skin, lungs, and heart only

^b Target Plaque Severity Score: Sum of erythema, induration, and scaling each scored 0-4 (maximum score = 12). Target plaque area = Longest diameter (cm) x Widest perpendicular diameter (cm). Up to three target plaques will be chosen, each at least 9 cm². The target plaques must each have a TPSS ≥ 4 . Subjects must have at least one target plaque.

^c Photography will be at selected investigational sites. Photography will be optional and confined to the target lesions. All efforts will be made to de-identify the subjects.

^d A urine pregnancy test will be administered to all females of child-bearing potential. A negative result is required for continued participation in the study, and results must be available prior to dispensing of study drug at each visit.

**STUDY EVENTS FLOW CHART: COHORT 2; 28 DAY APPLICATION TO 0.5 – 5% BSA;
DOUBLE BLIND, PLACEBO CONTROLLED (Continued)**

- e PK draws on day 1: 1, 2, 4 and 6 hours (\pm 10 minutes for 1, 2, 4 and 6 hour collections); day 14: pre-dose (trough) and 1-hour (\pm 10 minutes) post-dose; and day 28: pre-dose (trough), 1, 2, 4, 6 (\pm 10 minutes for 1, 2, 4 and 6 hour collections); and 24 hours (\pm 1 hour) post-dose for analysis. PKs will be collected from at least 45 volunteer subjects; PK collections will continue until PKs have been collected from 15 subjects in each treatment group.
- f Vehicle application training post baseline will be conducted as needed on Visits 3 (week 1) and 5 (week 3).
- g Drug or vehicle will be applied in clinic.
- h Visits 4 (week 2) and 6 (week 4) only: ARQ-151 cream or vehicle application will be done at home in the morning of Days 13 and 27 and in the morning at the clinic on PK collection Days 1, 14 and 28. ARQ-151 cream or vehicle will not be applied in the evening of Days 13 and 27.

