8.2.1 Dose Selection

The ARQ-151 cream 0.5% dose concentration was selected because of the efficacy observed in the Snape, et al study described above ([Snape 2016](#)). [REDACTED]

The dose concentration of ARQ-151 cream 0.15% was selected to determine whether lower ARQ-151 cream doses are effective and whether systemic exposure is also reduced.

Cohort 1 will involve application of ARQ-151 cream 0.5% to 25 cm² of psoriatic plaque(s). It is well known that cutaneous disease states can alter drug permeability as compared to normal human skin. Since psoriatic skin is known to have different drug permeability characteristics than normal skin ([Tang-Liu 1999](#)), we do not believe there is anything to be gained by prior application of topical drug to normal human volunteers. [REDACTED]

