9.1 Statistical Methods

The methodology presented below is a summary of the more detailed analysis plan that will be presented in the Statistical Analysis Plan (SAP). The SAP will be finalized before the database is locked and unblinded for Cohort 2. Any changes to the methods described in the final SAP will be described and justified in the clinical study report.

All statistical processing will be performed using SAS® (Version 9.4) unless otherwise stated. No interim efficacy analyses are planned.

Descriptive statistics will be used to provide an overview of the efficacy, safety and pharmacokinetic results. For categorical parameters, the number and percentage of subjects in each category will be presented. The denominator for percentage will be based on the number of subjects appropriate for the purpose of analysis. For continuous parameters, descriptive statistics will include n (number of subjects), mean, standard deviation (SD), median, minimum, and maximum.

P-values of less than 0.05 will be considered statistically significant based on a two-sided test unless otherwise specified.

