9.1.2 Subjects to Analyze

Safety population will include all subjects who are enrolled and received at least one confirmed dose of study medication. This population will be defined separately for each cohort.

The Modified Intent-to-Treatment (mITT) population will include all subjects who are in the safety population for Cohort 2 with at least one post-baseline efficacy evaluation.

Per-Protocol (PP) Population will include all subjects who are in the safety population for Cohort 2, were at least 80% compliant with study medication, and showed no other serious deviations from the study protocol.

The PK population will include all subjects receiving the active drug with sufficient plasma concentrations of roflumilast to define a profile, as determined by the pharmacokineticist. This population will be defined separately for each cohort.

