9.4 Pharmacokinetic Analysis

Pharmacokinetic parameter estimates for roflumilast will be calculated by a standard noncompartmental method of analysis; these may include AUC_{0-t} , AUC_{0-inf} , C_{max} , t_{max} , and others, as data permit. Pharmacokinetic parameters will be summarized using appropriate descriptive statistics. Time to reach maximum concentration (t_{max}) will be summarized using n, mean, standard deviation, median, minimum, and maximum. All other PK parameters will also be summarized using geometric mean and coefficient of variation.

For all subjects, blood samples for the determination of roflumilast and its metabolites will be collected at scheduled time points as delineated in the Schedule of Visits and Assessments (Section 6).

Note: the sample times for PK collection are in relation to the start of drug application.

A manual for blood sampling, collection, processing, and sample shipment will be provided in a separate document.

STUDY ADMINISTRATION

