11.1. Blood Pharmacokinetic Analysis

Blood samples for PK evaluation will be performed as follows:

Cohort 1: PK draws will be done at 1, 2, 4, 6, and 24 hours after ARQ-151 cream 0.5% application to 25 cm² of psoriatic plaque(s).

Cohort 2: PK draws will be done, for subjects consenting to PK draws, on Day 1: 1, 2, 4 and 6 hours; Day 14: pre-dose (trough) and 1 hour post-dose; and Day 28: pre-dose (trough), 1, 2, 4, 6 and 24 hours.

All PK collection information from the eCRF will be presented in a listing.

All PK analysis, including calculations of PK parameters and TLF production, will be performed by a PK vendor; those results will be presented in a separate PK report.

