GCP	good clinical practice
GMP	good manufacturing practices
GPV	global pharmacovigilance
HR	heart rate
IB	investigator's brochure
IC or ICF	informed consent or informed consent form
ICH	international council for harmonization

Statistical Analysis Plan,
 Sponsor Arcutis, Inc.
 Protocol Number ARQ-151-101
 PCN Number ARCU7063

Abbreviation	Definition
ID	identification
IDM	independent drug monitoring
IEC	independent ethics committee
IM	investigator meeting
IMV	interim monitoring visit
IND	investigational new drug
INDSR	investigational new drug safety reports
IP	investigational product
IRB	institutional review board
IRF	inventory release file
IRR	infusion related reactions
IRT	interactive response technology
ISF	investigator site file
ITT	intent-to-treat
IVRS	interactive voice response system
IWRS	interactive web response system
IxRS	interactive voice/web response system
KPI	key performance indicator
LAN	local area network

AD-ST-33.04 Effective date: 30-Jun-2017

Version 1.0 | Date 06-May-2018 | AD-PR-109.01 Effective date: 26-Jun-2017

Page 103 of 107

Abbreviation	Definition
LDM	lead data manager
LMS	learning management system
LLOQ	lower limit of quantification
LPI	last patient in
LPLV	last patient last visit
LPO	last patient out
MAAP	medical affairs and pharmacovigilance teams
MAH	marketing authorization holder
MedDRA	medical dictionary for regulatory activities
MHRA	medicines and healthcare products regulatory agency
MM	medical monitor
MMP	medical monitoring plan
MMRM	mixed effect model repeat measurement
MTD	maximum tolerated dose
MVR	monitoring visit report
N	number
NA	not applicable
NCS	non-clinically significant
NF	non-functional

Abbreviation	Definition
PD	protocol deviation
PDGP	protocol deviation guidance plan
PE	physical examination
PI	principal investigator
PIN	personal identification number
PK	pharmacokinetic
PKAP	pharmacokinetic analysis plan
PM	project manager
PMP	project management plan
PP	per-protocol
PRIMS	Premier Research information management system
PS	project specialist
PV	pharmacovigilance
PVG	pharmacovigilance group
QA	quality assurance
QARC	quality assurance, risk and compliance
QC	quality control
QOL	quality of life
ROT	record of training

Abbreviation	Definition
RR	respiratory rate or relative rate
RSM	regional site monitor
SAE	serious adverse event
SAP	statistical analysis plan
SAS®	a software system used for data analysis
SBP	systolic blood pressure
SC	study coordinator
SCR	software change request
SD	standard deviation

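### Does the undefined phrase 'sufficient plasma concentrations' in the PK population bias the reported exposure?

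*SAP*

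**What the plan says.** Protocol section 9.1.2 defines the PK population as "all subjects receiving the active drug with sufficient plasma concentrations of roflumilast to define a profile", on the pharmacokineticist's judgement. SAP section 5 repeats this for subjects who consented to PK draws: "receiving the active drug with sufficient plasma concentrations of roflumilast to define a profile, as determined by the pharmacokineticist". Neither gives a minimum number of samples, a quantification limit or a rule for results below it.

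The SAP keeps little of the PK work. Section 11.1 states: "All PK analysis, including calculations of PK parameters and TLF production, will be performed by a PK vendor", with results in a separate report. The term "pharmacokinetic analysis plan" appears in the CRO's general abbreviation list (SAP Appendix 1), but the SAP text cites no such plan.

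The planned use of the data is descriptive. Protocol section 9.1: "Descriptive statistics will be used to provide an overview of the efficacy, safety and pharmacokinetic results". Protocol section 9.4, after treating the time of maximum concentration separately: "All other PK parameters will also be summarized using geometric mean and coefficient of variation". On sample size, footnote e of the Cohort 2 flow chart in protocol section 6 says: "PK collections will continue until PKs have been collected from 15 subjects in each treatment group".

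**The concern.** PK is part of both primary objectives. Protocol section 8.2.1 says the 0.15% strength was included "to determine whether lower ARQ-151 cream doses are effective and whether systemic exposure is also reduced". An entry rule that depended on the measured level would select on the very quantity being summarised. Subjects with low or unquantifiable roflumilast would leave, and the mean of those who remained would be too high.

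If exposure is lower at 0.15%, that arm would tend to lose more subjects under a common cut-off, so the two strengths could look more alike than they are. With about 15 PK subjects per arm, each exclusion counts. The wording also leaves the decision to one expert and does not ask for it to be made before concentrations are seen by treatment.

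**Working it through.** **Counts from the plan.** Three groups of 15 give 3 × 15 = 45, which matches the Cohort 2 PK number in the protocol synopsis and section 8.15. Two of the groups receive active drug, so 30 subjects can enter the Cohort 2 PK population. Each has 4 draws on Day 1, 2 on Day 14 and 6 around Day 28: 4 + 2 + 6 = 12.

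**The two readings.**
- Enough evaluable samples: a subject leaves because draws were missed or unusable. This does not select on level, and the effect is zero.
- High enough levels: a subject leaves because concentrations are low. One low draw out of 12 need not remove anyone; the subject must be low across enough draws to lose the curve. For a summary to be affected it must also be restricted to this population, and neither protocol section 9.4 nor SAP section 2.2.3 names a population for it.

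**Illustration of the second reading.** The readable text gives no assay limit, expected concentration or PK variability (parts of protocol sections 8.1.1, 8.2.1 and 8.2.2 are blacked out). Everything below is therefore assumed: lognormal exposure, one value per subject, one cut-off for both arms, set so that k of 15 fall below it at 0.15%.

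Formulas: σ = √ln(1 + CV²). For an arm with log-mean μ and log cut-off c, let a = (c − μ)/σ. The geometric mean of those kept is exp[μ + σ·φ(a)/(1 − Φ(a))].

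Worked case: CV 100%, k = 3, true 0.15%/0.5% ratio 0.30.
- σ = √ln 2 = 0.833.
- 0.15% arm: a = −0.842 and φ(a) = 0.280, so inflation is exp(0.833 × 0.280/0.80) = 1.34.
- Log cut-off: ln 0.30 − 0.842 × 0.833 = −1.905.
- 0.5% arm: a = −1.905/0.833 = −2.29. About 1% is lost and inflation is 1.02.
- Displayed ratio: 0.30 × 1.338/1.025 = 0.39.

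Displayed geometric mean ratio, same CV in both arms (range over CV 70% to 150%):

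| True ratio | k = 1 | k = 2 | k = 3 |
|---|---|---|---|
| 0.30 | 0.33–0.34 | 0.35–0.38 | 0.37–0.41 |
| 0.50 | 0.54–0.56 | 0.57–0.59 | 0.60–0.63 |
| 0.70 | 0.74–0.75 | 0.77–0.78 | 0.79–0.80 |
| 1.00 | 1.00 | 1.00 | 1.00 |

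**The direction depends on equal spread.** Take CVs at opposite ends of the same range, k = 1 to 3:
- CV 70% at 0.15% and 150% at 0.5%: a true 1.00 shows as 0.76 to 0.71, and a true 0.70 as 0.60 to 0.59. The difference is exaggerated.
- CVs swapped: a true 1.00 shows as 1.15 to 1.33, and a true 0.90 as 1.04 to 1.22. The order is reversed.

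Attenuation is also not confined to lower exposure at 0.15%. With equal CV 100% and a cut-off at 0.3 times the 0.5% geometric mean, a true 1.50 shows as 1.39.

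**Against sampling error.** With 15 per arm the 95% limits of a geometric mean ratio lie a factor exp(1.96·σ·√(2/15)) either side: 1.57, 1.81 and 2.17 at CV 70%, 100% and 150%. The equal-spread shift for a true 0.30 with k = 3 is a factor of 0.372/0.30 = 1.24, 0.392/0.30 = 1.31 and 0.411/0.30 = 1.37 at the same CVs.

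**Keeping everyone and substituting.** For a true 0.30, CV 100% and k = 3, replacing values below the limit by the limit, half of it or a tenth of it gives a geometric mean ratio of 0.33, 0.29 or 0.21. The last is 29% too low, against 31% too high (0.39) when those subjects are excluded.

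**The case for a change.** The best case for a change is this. The SAP calls itself an a priori plan, this is its only PK population, and the phrase speaks of concentrations rather than samples. Consent is listed separately, so the phrase must do some further selecting. Population counts by treatment (SAP section 7.1) and Listings 16.2.3 and 16.2.5.4 would make a loss visible but would not correct it. The remedy is cheap: admit anyone on active drug with one evaluable post-dose sample at any level, fix a rule for results below quantification, and show the median beside the geometric mean.

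What stands: the wording is ambiguous in both documents, and a level-based exclusion would overstate mean exposure in any arm that lost subjects.

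What does not: defining a profile describes a concentration–time curve, so a sample-count reading is at least as natural. That the SAP states no rule does not show that none exists, because PK analysis and its outputs sit in a vendor report that was not available here. The predicted shrinkage of the contrast needs a common cut-off and equal spread. A substitution rule can move the geometric mean ratio about as far as the bias it removes. The median avoids this only while fewer than half of an arm lies below the limit.

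**Conclusion.** No change to the plan is needed. This is missing detail that a pharmacokineticist would ordinarily fill sensibly when preparing the vendor's analysis.

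The effect is zero if the phrase means enough evaluable samples. Otherwise its size and direction cannot be determined from the documents. The figure of 0.33 to 0.41 for a true ratio of 0.30 rests wholly on the assumed lognormal model, common cut-off, equal spread and 1 to 3 losses out of 15.

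The consequences are limited on any reading. Neither document plans a formal PK comparison between strengths, the efficacy populations do not depend on PK, overstated exposure is the cautious direction for safety, and the number in each population will be reported by treatment.

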6.1. Statistical Definitions and Algorithms

6.1.1. Baseline

The last observation recorded before the first dose of study drug in each cohort will be used as the baseline observation for all calculations of change from baseline.

6.1.2. Adjustments for Covariates

Where statistical modelling is performed, the baseline value of that assessment will be used as a covariate.

6.1.3. Multiple Comparisons

The type I error rate of $\alpha = 0.05$ will be maintained for the entirety of the primary endpoint by using the Bonferroni method to control for multiplicity, where the significance level for each of the 2 comparisons of active versus placebo is $\alpha = 0.025$.

No adjustments will be made for multiple comparisons for other endpoints; all analyses will be conducted at the $\alpha = 0.05$ level.

6.1.4. Handling of Dropouts or Missing Data

Any subject who withdraws from the study may be replaced at the discretion of the Sponsor. For AEs, if severity or relationship to study drug is missing, then it will be treated as missing. In general, missing data will not be imputed, except as described in [Section 6.1.8](#).

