9.3 Safety Evaluation

The following analyses will be performed; however, no formal inferential statistics will be performed on safety assessments.

Descriptive statistics will be calculated for quantitative safety data and frequency counts will be compiled for classification of qualitative safety data.

Adverse Events:

The assessment of safety will be based mainly on the frequency and percent of subjects who reported treatment-emergent AEs.

Adverse events will be coded using the Medical Dictionary for Drug Regulatory Activities (MedDRA) Version 18.1 or higher. Treatment emergent adverse events (i.e. events with onset dates on or after the start of study drug or with missing onset dates) will be summarized by presenting for each treatment group, the number and percentage of subjects having any AE, having an AE in an individual body system, and having an AE in an individual preferred term. Any other information collected (e.g. severity or relatedness to study medication) will be listed as appropriate.

Application Site Reaction

The numeric application site reaction scores will be summarized individually by using number and percentage of subjects by visit.

Medical History and Physical Examinations:

Medical history for all subjects will be presented in a by-subject listing.

Physical examination findings for all subjects will be presented in a by-subject listing. Changes in physical examinations will be described in the text of the final report.

Clinical Laboratory Results, Electrocardiograms and Vital Signs Measurements:12

All clinical laboratory results, 12-lead ECGs and vital signs measurements and their change from baseline (pre-dose), will be summarized along with time point of collection.

A shift table describing out-of-normal range shifts will be provided for clinical laboratory results.

Prior and Concomitant Medications:

Prior and concomitant medication information for all randomized subjects will be presented in a by-subject listing. Summary tables will be presented by World Health Organization-Anatomical Therapeutic Chemical Classification System (WHO-ATC) therapeutic category and product.

Quick Inventory of Depressive Symptomatology-Self-Report (QIDS-SR):

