6.1.8. Data Adjustments/Handling/Conventions

All collected data will be presented in listings. Data not subject to analysis according to this plan will not appear in any tables or graphs but will be included only in the data listings.

All p-values will be displayed in 4 decimals and rounded using standard scientific notation (eg, 0.XXXX). If a p-value less than 0.0001 occurs, it will be shown in tables as <0.0001.

All AEs and medical histories will be coded using the Medical Dictionary for Regulatory Activities (MedDRA) version 20.1 thesaurus. Prior and concomitant medications will be coded using the World Health Organization-Drug Dictionary Enhanced (WHO-DDE) version September 2017.

A treatment related AE is any AE with a relationship to the study drug of possibly, probably, or likely related.

If partial dates occur, the convention for replacing missing dates for the purpose of statistical analysis is as follows:

For partial AE and medication start dates:

- if just day is missing then the day assigned is the first day of the month or the date of first dose (if in the same month), whichever is later;

- if just month is missing then the month assigned is the month of the first dose, unless that results in a date prior to the first dose in which case the month after the first dose is used; and
- if both month and day are missing then the month assigned is the month of the first dose and the day assigned is the first dose day.

For partial AE and medication end dates:

- if just day is missing then the day assigned is the day of the last date on study (ie, date of last contact if subject lost to follow-up or date of completion / early termination) if month and year do match the month and year of the last date of the study, or the last day of the month otherwise;
- if just month is missing then the month assigned is the month of the last date on study, unless that results in a date after the last date on study, in which case the month before the last date on study is used; and
- if both month and day are missing then the month assigned is the month of the last date on study and the day assigned is the day of last date on study, unless that results in a date after the last date on study, in which case the first day of the month is assigned.

If partial times occur, the convention is as follows:

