9.1. Adverse Events

An event that is temporally associated with administration of study product is defined as a treatment emergent adverse event (TEAE). Events meeting this definition will be those with a start date during or after administration of the first dose of study drug through the telephone follow-up in each cohort. For AEs occurring on the date of the first dose of study drug, if the time of onset is missing, the AE will be assumed to be treatment emergent.

The causal relationship of the AE to the study drug is determined by the investigator as Unrelated, Unlikely Related, Possibly Related, Probably Related, and Likely Related. These can be mapped to Unrelated (*Unrelated* and *Unlikely Related*) and Related (*Possibly Related*, *Probably Related*, and *Likely Related*).

Adverse event severity grades are reported on a 5-point scale of Grade 1 (*Mild*), Grade 2 (*Moderate*), Grade 3 (*Severe*), Grade 4 (*Life-threatening consequences*), or Grade 5 (*Death related to AE*).

An AE summary table will be presented for the following:

AD-ST-33.04 Effective date: 30-Jun-2017

- All TEAEs
- TEAEs by maximum severity
- Treatment-related TEAE
- TEAEs leading to discontinuation of study drug
- Serious AEs (SAEs)
- Deaths

Summaries of incidence rates (frequencies and percentages) of individual TEAEs by MedDRA (v20.1) system organ class (SOC) and preferred term (PT). Such summaries will be displayed for all TEAEs, TEAEs by maximum severity, and treatment-related. Analysis of TEAEs will be performed by treatment within cohort.

Each subject will be counted only once within each summation level (SOC and preferred term). If a subject experiences more than 1 TEAE within each summation level only, the TEAE with the strongest relationship or the maximum severity, as appropriate, will be included in the summaries of relationship and severity.

Incidence will be presented by descending frequency of SOC and PT within SOC, and then alphabetically within PT where the incidence is the same; this is based on overall subjects.

Missing and partially missing AE start and/or stop dates will be imputed, for the purpose of statistical analysis, according to the specifications described in [Section 6.1.8](#).

In the AE data listings, all AEs will be displayed. AEs that are treatment emergent will be flagged.

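### A TEAE with no recorded relationship can never count as treatment-related, so the within-arm related rate can only be understated; SAP 6.1.4 should state a convention

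*SAP*

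**What the plan says.** SAP 6.1.4 (Handling of Dropouts or Missing Data) gives the rule for the two investigator-assigned AE attributes: "For AEs, if severity or relationship to study drug is missing, then it will be treated as missing". It then adds a general rule: "In general, missing data will not be imputed, except as described in" Section 6.1.8. For AEs, Section 6.1.8 fills in only partial dates and times.

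SAP 6.1.8 defines relatedness by a closed list: "A treatment related AE is any AE with a relationship to the study drug of possibly, probably, or likely related". SAP 9.1 maps the five recorded relationship categories to Related or Unrelated and has no entry for a blank.

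On the tables by system organ class (SOC) and preferred term (PT), SAP 9.1 says: "Such summaries will be displayed for all TEAEs, TEAEs by maximum severity, and treatment-related". A subject with several TEAEs at one level is counted once: "the TEAE with the strongest relationship or the maximum severity, as appropriate, will be included in the summaries of relationship and severity". The SAP does not say how a missing value ranks in that choice. For the listings it says: "In the AE data listings, all AEs will be displayed".

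Missing onset information is handled cautiously. Protocol 9.3 defines treatment-emergent AEs as "events with onset dates on or after the start of study drug or with missing onset dates". SAP 9.1 says of an AE on the first-dose date: "if the time of onset is missing, the AE will be assumed to be treatment emergent".

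**The concern.** When onset timing is uncertain, the plan keeps the event in the treatment-emergent count. When relationship is unknown, the SAP's definition leaves the event out of the related count. No cautious convention, sensitivity analysis or count of affected events is planned for relationship or severity.

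Safety is a primary objective in both cohorts (SAP 2.1.1), and this is the first study of the topical product in humans (Protocol 8.1.2). No inferential safety statistics are planned (SAP section 9), so the counts themselves are what a reader will use, and the denominators are small. Cohort 1 is open label with one treatment (SAP 3.4 and 3.6), so it has no control arm against which to judge an understated related rate.

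**Working it through.** The documents give no figure for this rule, so there is none to reproduce. The check traces the rule through the definitions and then sizes one affected subject.

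**Step 1: relationship.** SAP 6.1.4 leaves a blank as a blank. SAP 6.1.8 admits only the three upper categories as related, and SAP 9.1 maps only recorded categories. A TEAE with a blank relationship therefore cannot enter Table 14.3.1.4 or the treatment-related line of the AE summary table. It remains in the all-TEAE tables and in the listings.

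**Step 2: when a subject is lost from the count.** Each subject counts once per level. A blank changes the overall related rate only if that subject has no other related TEAE. It changes an SOC or PT row only if the subject has no other related TEAE in that row.

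**Step 3: size of one step.**
- Cohort 2: 84 subjects (SAP 3.2) allocated 1:1:1 (SAP 3.5) give 84/3 = 28 per arm, assuming that all are dosed as randomized.
- One subject: 1/28 = 3.6 points. Two: 2/28 = 7.1. Three: 3/28 = 10.7.
- Cohort 1: up to 8 subjects (SAP 3.1). At the full 8, one subject is 1/8 = 12.5 points. This is the smallest possible step, because fewer subjects make it larger.
- All-TEAE incidence: a change of 0.0 points in every case.

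**Step 4: the comparison with vehicle.** The documents give no expected related rates, so this example is assumed: 6/28 related on active (21.4%) and 3/28 on vehicle (10.7%), with every affected subject having no other related TEAE.

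| Subjects lost to a blank relationship | Active | Vehicle | Difference (points) |
|---|---|---|---|
| None | 6/28 = 21.4% | 3/28 = 10.7% | 3/28 = 10.7 |
| One on active | 5/28 = 17.9% | 3/28 = 10.7% | 2/28 = 7.1 |
| One on vehicle | 6/28 = 21.4% | 2/28 = 7.1% | 4/28 = 14.3 |
| One on each | 5/28 = 17.9% | 2/28 = 7.1% | 3/28 = 10.7 |

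Within an arm the rate moves only downwards. The difference can shrink, grow or stay the same.

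**Step 5: severity.** SAP 6.1.4 and 9.1 do not say whether an ungraded TEAE is left out of the maximum-severity table, shown in a row of its own, or passed over when the subject has another graded event. The table shells have been removed from the public SAP, so this cannot be settled from the documents.

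**The case against.** The strongest reply is that the SAP openly states a neutral rule: it does not invent a causality judgement that the investigator did not make. Blanks should also be rare. Protocol 8.16.1.4 requires the investigator to assess relationship and grade every event. Protocol 9.7 provides a 100% quality check and edit checks for missing data, with corrections before lock. Protocol 9.3 rests the safety assessment mainly on overall TEAE frequency and promises only listings for severity and relatedness. All of this stands, and it keeps the point small. It does not make the rule moot, because SAP 6.1.4 governs whatever is still blank after cleaning.

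A reader might infer three stronger things that the documents do not support.

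- **That the safety summary as a whole errs in the favourable direction.** The all-TEAE, SAE and discontinuation tables use neither attribute, all AEs are listed, and Step 4 shows no fixed direction against vehicle.
- **That an ungraded AE drops out of the maximum-severity table, or that a milder event replaces it.** Treating a grade as missing is compatible with a separate row for missing grades, and the shells are not available to show otherwise.
- **That a missing grade should be set to Grade 3.** Nothing in the documents supports that grade. It could tabulate a trivial event as severe, adding up to 3.6 points per subject in an arm of 28.

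Nor is this a conflict between a cautious protocol and an incautious SAP. The SAP is itself cautious on onset timing, so the contrast is between how it treats timing and how it treats relationship.

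**Conclusion.** The point holds for relationship. Under SAP 6.1.4, 6.1.8 and 9.1 together, a TEAE without a recorded relationship is never counted as treatment-related, so the within-arm related rate is either unaffected or understated. The size is 3.6 points per affected subject in a Cohort 2 arm and 12.5 points in a full Cohort 1. This assumes that the planned numbers are dosed and that the subject has no other related TEAE. The effect is zero if nothing is missing at lock, and the documents give no reason to expect many blanks.

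For severity, the conclusion is only that the handling is unspecified in the text available. This is a cheap improvement and does not threaten the safety conclusions.

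**What to change.** Replace the AE sentence in SAP 6.1.4 with, for example: 'In summary tables, a TEAE with missing relationship is counted as related. In the maximum-severity table, a missing severity is shown in a separate Missing row and is not imputed. A footnote gives the number of such events by arm. Listings show the value as missing.' The text should also say how a missing grade ranks when the same subject has a graded event at the same level.

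The cost is a few lines of SAP text, one table row and a footnote. The related count may become slightly less favourable, and an event that was truly unrelated would be counted as related. The footnote lets a reader see how many events this concerns.
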